A phase II trial of temozolomide followed by high dose IL-2 was conducted by UPMC (6). This study concluded that although it was safe to combine these agents and the combination had lower toxicity than previous biochemotherapy regimens, the overall response rates and durability of responses did not exceed those of single agent high dose IL-2. In this study, the patients received temozolomide at 75 mg/m² for 3 weeks continuously followed by high dose IL-2 off the temozolomide. This was repeated again and then response was determined. Responding and non-progressing patients received repeated courses up to 4 maximum. A course consisted of 2 cycles of high dose IL-2 as noted above with temozolomide for 21 days prior to each cycle. The overall response rate for the trial was 16.1%. CR rate was 9.7% and PR rate was 6.5%. Two of the 3 CR patients had durable responses. As noted, in this trial the temozolomide was given before the IL-2. We have reasons to suspect that the sequence of the two drugs as therapy would be crucial for response and indeed that is what led to the design of the current trial described below.

1.2 Rationale for Sequence-Specific Combination of High Dose IL-2 and Temozolomide in Metastatic Melanoma

As noted, we have recently observed that many patients who had received high dose IL-2 and failed to respond to it but who then go immediately to temozolomide seemed to enjoy extremely good responses which seem better quality and longer duration than typically observed for temozolomide alone. To date, we have observed 5 sequentially treated patients with metastatic melanoma who had failed high dose IL-2 but who then went on to receive immediate temozolomide given at 75 mg/m² per day for 21/28 days (7). Two of these patients had CRs, and 3 had very strong PRs. One CR has been durable to date which is a marked anomaly for single agent temozolomide. For comparison, in a recent phase II of extended low dose temozolomide alone given in the same manner as to the post-IL-2 patients noted above, the response rate was 12.5% and all of these were partial responses only. The median time to progression was 3.3 months (8). The responses that we observed were at a much higher rate of response as well as much better quality than expected for temozolomide alone as noted above. The responses were

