progression for at least eight weeks at the time of enrollment. Patients must not require corticosteroids for treatment of cerebral edema for brain metastases. Patients must be evaluated with a head MRI within 4 weeks prior to enrollment. Patients may have had prior dacarbazine or temozolomide since the mechanism of action of the temozolomide to be used in the context of this study is related more to effects on immune cells than to its known anti-melanoma effects. Patients would receive baseline staging imaging and laboratory assessment including study-specific immunologic correlative science testing. Patients would receive HD IL-2 according to standard procedure as in-patients on the PSHCI inpatient clinical unit. Patients would receive Cycle 1 of aldesleukin at 600,000 International Units/kg every 8 hours as tolerated up to a maximum of 14 doses. On or about day 10 after discharge from Cycle 1, they would be re-admitted for Cycle 2 of treatment. Then, 28 days after discharge from Cycle 2, they would receive temozolomide at 75 mg/m² daily for 21 days. Two cycles of HD IL-2 therapy as performed above plus 21 days of temozolomide would constitute one course of therapy. After this they would be scanned to assess response with CT/PET or CT(CAP). Responding patients (CR, PR, SD, Minor Response) would be given a 2nd course of treatment as above. Patients with a CR would receive one additional course of treatment and would then be observed. Patients with SD after 2nd course of treatment would go off study. Patients with a PR or Minor Response would continue treatment up to a maximum of 4 courses (8 cycles). If they develop Progressive Disease at any time during this treatment then they would go off study. If they develop a CR then they would have one additional course of treatment provided this course does not make more than 4 total courses. If they have PR or Minor Response after Course 2 then they would receive up to 2 additional courses.

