2.0 STUDY OBJECTIVES

2.1 Primary Objectives:

- 1) To determine the clinical response (complete response, partial response, minor response, stable disease or disease progression) to high dose IL-2 followed by low dose temozolomide.
- 2) To determine the duration of response, and safety and toxicity of high dose IL-2 followed by low dose temozolomide.

2.2 Secondary Objectives:

- 1) To determine the quantitative effects of high dose IL-2 followed by low dose temozolomide on lymphocyte subsets, particularly the T-reg cells.
- 2) To determine the quantitative effects of high dose IL-2 followed by low dose temozolomide on cytokine production and anti-melanoma specific T-cell immune cells.
- 3) To determine the effects of high dose IL-2 followed by low dose temozolomide on autoimmune laboratory markers and clinical manifestations of autoimmunity.

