or MR) then accrual of an additional 25 patients will ensue. Three additional patients would be allowed to accrue to cover any early drop-outs (receipt of less than 2 complete cycles of treatment). Eligible patients would have baseline imaging with CT or CT/PET. A head MRI to rule out asymptomatic occult brain metastases will be performed on all patients as well. Patients with known brain metastases will have baseline MRI done as well and would then have follow-up MRIs performed after each course. An echocardiogram to check cardiac function and PFTs with DLCO will be performed in all patients to assure that they have adequate cardiopulmonary reserve to sustain HD IL-2 as is standard. Patients would have baseline laboratory testing done pre-treatment and at every cycle initiation. An autoimmune panel will be performed pre-treatment and after every cycle of treatment. Correlative science immunoassays will be performed pre-treatment and after every cycle of treatment. Response as per radiologic imaging assessment and physical assessment of accessible and measurable skin metastases if applicable will be performed after every course of treatment (2 cycles HD IL-2 and 21 days of temozolomide.). Response will be determined after course 1 of treatment as a complete response (CR), partial response (PR), minor response (MR), stable disease (SD) or progressive disease (PD) according to standard definitions of response. Patients with CR will receive another complete course of treatment and will then go off study except for follow-up. Patients with progressive disease (PD) will go off study after course 1. Patients with stable disease (SD) after course one will repeat one additional course maximum. Patients with PR or MR will continue with additional courses as determined by response up to a maximum of 4 courses total (8 cycles). Responses and their durability will be compared to known rates of response and their durability using HD IL-2 alone. For a population of 40, using standard HD IL-2, the expected response rate 10% would be in 4 of the 40 and the CR rate 5% in about 2 of the 40. We would hypothesize that we can at least double these at a minimum using the methods described in this protocol.

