4.1.1 Aldesleukin Dosage, Administration and Dose Modifications

The dose of IL-2 is 600,000 International Units/kg given intravenously every 8 hours as tolerated by the Pittsburgh clinical guidelines for management up to a maximum of 14 doses. Patients rarely get to 14 doses. Patients are supported symptomatically and with fluid boluses. Vasopressors are not used. No dose modifications are utilized. Doses are held per the clinical guidelines.

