5.3 Therapy

After baseline studies have been completed, the patients would be admitted to the PSHCI inpatient clinical unit for Course 1 Cycle 1 of HD IL-2 treatment. Treatment will proceed according to the standard treatment algorithm utilized by the PSHCI inpatient clinical unit. Patients will be given as many doses of IL-2 up to a maximum of 14 at 8 hr intervals as allowed by the algorithm at 600,000 International Units/kg. Patients will receive standard supportive measures including fluid boluses, antiemetics and antipyretics as indicated. The patients will be discharged when the acute toxicities of the IL-2 have subsided. They will be reassessed on or about Day 10 after discharge from Cycle 1 and will be re-admitted for Cycle 2. After Cycle 2 of HD IL-2, they would begin temozolomide at 75 mg/m² on the 28th day after discharge and they would take it daily at bedtime for 21 days. Approximately 14 days after the final dose of temozolomide, patients will be assessed for response via imaging. The response determined after restaging post course 1 would determine the next step. Patients with progressive disease would go off study. Patients with a CR would receive one additional course of treatment and would then be observed. Patients with SD would receive one additional course of treatment. Patients with a PR or minor response would continue treatment up to a maximum of 4 courses (8 cycles HD IL-2 and 4 cycles of temozolomide). If they develop progressive disease at any time during this treatment then they would go off study. If they develop a CR then they would have one additional course of treatment provided this course does not make more than 4 total courses. If they have PR or minor response after course 2 then they would receive up to 2 additional courses.

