8.2 Efficacy Determination

Efficacy analysis will be performed on the intention-to-treat set, which comprises of all patients enrolled in the trial. Patients must have completed at least one complete course (2 cycles) to be considered for response assessment. Patients receiving less than one course will be considered drop-outs from the study in terms of response. Patients who do complete at least one course of treatment will be classified as responders or non-responders. The overall response rate, which is the proportion of the responses among patients in the intention-to-treat set who have completed at least one complete course, will be obtained. In addition, a 95% confidence interval for the overall response rate will be constructed. Responses will be recorded after each course of therapy and will be tabulated as complete response, partial response, minor response, stable disease or progressive disease. Only PR and CR will be included in the numerator of the analysis for overall response but all responses will be recorded. The time to progression (TTP) in months for each patient will be recorded to ascertain the durability of the responses. Waterfall plots for a continuous assessment of response will also be generated. Correlative science results will be studied by non-parametric methods for differences in a given individual over time and between individuals.

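### Duration of response is part of primary objective 2, but section 8.2 measures durability only by time to progression in every patient, with no origin, responder restriction, censoring rule or summary method

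*Combined protocol and SAP*

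**What the plan says.** Section 2.1 lists as primary objective 2: "To determine the duration of response, and safety and toxicity of high dose IL-2 followed by low dose temozolomide". The only provision for it in the statistical section is the sentence in 8.2: "The time to progression (TTP) in months for each patient will be recorded to ascertain the durability of the responses".

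Section 3.0 adds a use for the result: "Responses and their durability will be compared to known rates of response and their durability using HD IL-2 alone". It names no method and no historical durability figure.

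Other sections supply some of what 8.2 lacks, but not the essentials:

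- Section 5.6 names TTP, progression-free survival and overall survival as follow-up outcomes, taken from patient records at intervals of generally six months or less. It defines none of them.
- Section 6.1 defines progressive disease and best response, so the progression event exists. It does not define duration of response.
- Section 8.2 counts only CR and PR in the overall response rate. The stage 1 rule in 3.0 also counts minor response (MR), and the synopsis in 1.3 lists stable disease (SD) among responding patients.

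**The concern.** Duration of response and TTP are different quantities. The first is measured in responders only and starts when the response is documented. The second, as 8.2 sets it out, is recorded in everyone. Patients who never respond have no response date, so a single TTP definition that covers all patients most naturally starts at enrolment or first treatment. A responder's TTP then includes all the time before the response was seen. A summary over all patients would mainly describe non-responders.

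The missing censoring rule matters because the rationale in 1.2 hopes for complete responses that last. Those patients may not have progressed by the time of analysis, and the plan gives them no value. With origin, population and censoring all open, the choices could be made after the data are seen, on part of a primary objective.

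**Working it through.** **1. Difference between the two measures.** For a responder who progresses:

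- TTP = progression date − origin
- Duration of response = progression date − date of first documented CR or PR
- Excess = TTP − duration = date of first documented CR or PR − origin

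The excess does not depend on when the patient progresses. It is zero if the origin is first response. If the origin is start of treatment (assumed), it equals the time to the scan that first shows CR or PR.

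**2. Time to the first scan.** Section 6.1 and the flow chart put one course, up to reimaging, at about 12 weeks. As a check, the scheduled intervals in 5.3 are:

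- discharge from cycle 1 to cycle 2: about 10 days ("They will be reassessed on or about Day 10 after discharge from Cycle 1 and will be re-admitted for Cycle 2")
- discharge from cycle 2 to first temozolomide dose: 28 days
- first to 21st daily temozolomide dose: 20 days
- last dose to imaging: about 14 days

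Sum: 10 + 28 + 20 + 14 = 72 days = 10.3 weeks = 2.4 months (30.44 days per month).

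The two inpatient stays come on top. With 14 doses at 8-hour intervals and one day to discharge (assumed), each stay is 13 × 8 / 24 + 1 = 5.33 days, so the course is 72 + 2 × 5.33 = 82.7 days = 11.8 weeks. Section 4.1.1 notes "Patients rarely get to 14 doses". With 8 doses per cycle (illustrative), each stay is 7 × 8 / 24 + 1 = 3.33 days, and the course is 72 + 2 × 3.33 = 78.7 days = 11.2 weeks. The stated 12 weeks is a fair rounding.

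**3. Excess by scan of first CR or PR** (84 days per course, no gap between courses, origin at start of treatment; all assumed):

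| First CR/PR seen after | Days | Weeks | Months |
|---|---|---|---|
| Course 1 | 84 | 12 | 2.8 |
| Course 2 | 168 | 24 | 5.5 |
| Course 3 | 252 | 36 | 8.3 |
| Course 4 | 336 | 48 | 11.0 |

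The course 2 row applies to patients with SD or MR after course 1. The last two rows are narrow cases. Section 1.3 says "Patients with SD after 2nd course of treatment would go off study" and "If they have PR or Minor Response after Course 2 then they would receive up to 2 additional courses", so a first CR or PR at the course 3 scan requires MR after course 2. At the course 4 scan it also requires that course 3 showed neither CR nor PR and that treatment continued.

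An origin at enrolment adds any delay between enrolment and first treatment. The documents do not state that delay.

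**4. How many patients have a duration of response.** With 37 planned patients, 0.20 × 37 = 7.4 responders at the target rate. The success threshold in 8.1 is 4. An all-patient TTP would therefore contain about 30 non-responders at the target rate (37 − 7.4 = 29.6), or 33 at the threshold.

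**5. Decision rule.** The design in 8.1 (stop at 0 of 12, success at 4 or more of 37) reproduces as Simon's optimal design, with exact type I error 0.0935 and power 0.9024. It uses response counts only, so nothing above changes it. The plan states no duration figure to reproduce.

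**The case against.** The strongest reply is that 8.2 is under-specified rather than wrong. Its stated purpose is the durability of responses, response is recorded after every course, and nothing forbids starting the clock at first response or summarising responders alone. On that reading the excess is zero. It stands that the text does not exclude this and that the data for a proper duration of response will exist. It does not rescue the sentence as written, because a measure recorded for each patient cannot start at a response that most of them will not have.

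A second reply is that the background sections mostly use durability to mean the share of complete responses that last, and a shift of some months in the origin hardly alters that share. This is fair for the background, but objective 2 asks for duration and 8.2 records months.

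A reader might go further and infer that the comparison with high dose IL-2 in 3.0 is biased in favour of the new sequence. The documents do not support that. It would require both an early TTP origin here and a historical figure that is a duration of response, and neither is stated. The only numerical durability figure cited is in section 1.2: "The median time to progression was 3.3 months". That is a TTP, for temozolomide alone, so it does not settle what the IL-2 figure is. Comparing TTP with TTP from the same origin would carry no such bias.

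A reader might also take the 72 days per course as a minimum. It is not one, because two of its four intervals are stated only approximately.

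**Conclusion.** The point holds as a gap in the definition and analysis of part of a primary objective. Followed literally, 8.2 times a longer interval than the one the objective names. The excess is roughly 12 weeks for a CR or PR first seen after course 1 and roughly 24 weeks after course 2. These sizes rest on an origin at enrolment or start of treatment, which is the natural reading of an all-patient measure but is not stated, and on a course of about 12 weeks with no gap between courses.

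The text does not establish a biased comparison with historical IL-2, and it gives no reason to doubt the efficacy decision in 8.1. The change is worth making because it is cheap, but the gap does not undermine the trial.

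**What to change.** In 8.2:

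- Define duration of response, for patients with CR or PR, as the time from first documented CR or PR to progression or death. Censor patients without an event at their last disease assessment.
- Report it by Kaplan-Meier with a per-responder listing of response and progression dates. With 4 to 7 responders the listing may be as informative as the curve.
- Keep TTP as a separate measure with a stated origin, event and censoring rule, including how deaths without progression are handled. Counting death as an event for duration but censoring it for TTP is a choice, so it should be written down.
- State how new therapy after leaving the study is handled in both analyses.
- Compare with historical high dose IL-2 durability only where the definitions match, and say which measure the historical figure uses.

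This costs some wording and minor analysis work, since response after each course and progression are already to be recorded. The quoted duration will be shorter than a TTP counted from enrolment or treatment start, and it will be imprecise. Progression dates after patients leave the study remain coarse under record review, whichever measure is used.

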9.0 QUALITY CONTROL AND QUALITY ASSURANCE

The investigator is obligated to conduct this study in accordance with federal regulation 21 CFR 312.60-69 as specified on the signed form FDA 1572, applicable state laws, and the International Conference on Harmonization: Good Clinical Practice (GCP): Consolidation Guideline. Data will be collected in accordance with applicable regulations, GCP, and Penn State Milton S Hershey Medical Center procedures.

Data generated by the methods described in the protocol will be recorded on forms maintained in the patient research folders. It will be liable for audit by the IRB, FDA or other approved licensing agencies.

10.0 DATA HANDLING AND RECORD KEEPING

Records will be maintained by the Clinical Trials Office personnel who will retrieve the data from source clinical documents and place these data on the study forms. They will be locked and only available to study personnel. The data within the study forms will be entered into a data base (Oncore System) which will also only be available to study personnel.

Inclusion criteria - *Subjects must fulfill all inclusion criteria to be included in the study.*

	YES	NO
1. Provision of written informed consent.		
2. Metastatic malignant melanoma, pathologically		
3. Age \geq 18 years and ability to provide informed consent		
4. Patients should be considered ECOG <2 , Creat <2 , Bili <2 for conventional high dose IL-2		
5. No chemotherapy, hormonal therapy, immunotherapy or radiation therapy within 1 month of entry		
6. Patients with a history or clinical evidence of brain metastasis must have completed radiation therapy or surgical treatment of brain lesions and have no evidence of CNS progression for at least eight weeks at the time of enrollment. Patients must not require corticosteroids for treatment of cerebral edema for brain metastases. Patients must be evaluated with a head MRI within 4 weeks prior to enrollment.		
7. Patients may have had prior high dose IL-2 or temozolomide but not together or with high dose IL-2 followed by temozolomide		
8. Patients may have had prior high dose interferon as adjuvant treatment for high risk melanoma		
9. Serum Cr <2 mg/dL		
10. Bilirubin <2 mg/dL (except for Gilbert's Syndrome)		

Exclusion criteria- *The following criteria are considered to be exclusionary for Subjects to be considered for inclusion in the study:*

	YES	NO
1. Inability to provide informed consent.		
2. Hypersensitivity to temozolomide or HD IL-2		

- | | | |
|--|--------------------------|--------------------------|
| 3. Acute gastrointestinal disorders, or cardiac disorders i.e. cardiac failure, MI within 6 months as determined by the investigator |  |  |
| 4. EF < 50% by echo or corrected DLCO < 50% on diffusion capacity testing PFTs |  |  |
| 5. PLT < 100K, ANC < 1000 |  |  |
| 6. Chronic use of steroids other than for simple adrenal replacement |  |  |

Off Study Form

Dear _____:

It has been unfortunate that you wish to stop your participation in the Phase II Trial of High Dose Interleukin-2 followed by intermittent low dose Temozolomide in patients with Metastatic Malignant Melanoma. In order to complete our records, as requested by the trial, I would appreciate you indicating your interest below.

If you have any questions or wish to schedule a meeting, please call me at [name]. Thank you for your participation in the Phase II Trial of High Dose Interleukin-2 followed by intermittent low dose Temozolomide in patients with Metastatic Malignant Melanoma.

Sincerely,

[name], RN
Clinical Trials Coordinator

Check what contact you would like:

- I, _____, wish to continue my treatment in the Phase II Trial of High Dose Interleukin-2 followed by intermittent low dose Temozolomide in patients with Metastatic Malignant Melanoma.
- I, _____, do not wish to continue my treatment in the Phase II Trial of High Dose Interleukin-2 followed by intermittent low dose Temozolomide in patients with Metastatic Malignant Melanoma but wish to continue with **Direct** follow-up.
- I, _____, do not wish to continue my treatment in the Phase II Trial of High Dose Interleukin-2 followed by intermittent low dose Temozolomide in patients with Metastatic Malignant Melanoma but agree to continue with **Indirect** follow-up contact. HMC may contact my Physicians office for medical records.
- I, _____, do not wish to continue my participation in the Phase II Trial of High Dose Interleukin-2 followed by intermittent low dose Temozolomide in patients with Metastatic Malignant

ACTIVE TREATMENT FLOW CHART/TIME AND EVENTS SCHEDULE

TREATMENT:

Procedure	Baseline ¹	Pre-IL-2 Cycle 1	Post-IL-2 Cycle 1	Pre-IL-2 Cycle 2	Post-IL-2 Cycle 2	Temozolomide Day 1 (-2/+0 days)	Post Course ⁶
Informed consent	X						
Inclusion/exclusion criteria	X						
H&P	X	X		X			X
PET/CT scan or CT(CAP)	X						X
MRI of head ²	X						X
Echo/PFT	X						
Autoimmune panel ³	X		X ⁸		X ⁸	X ⁷	X
Immunoassays ⁴	X		X ⁸		X ⁸	X	X
Routine Labs ⁵	X	X		X		X	X

¹ – Baseline within 28 days of starting treatment

² – Patients with or without known brain metastases can get an MRI at any time, should they develop neurological Symptoms as determined by the investigator

³ – Will include ESR, CRP, ANA, RF and TSH

⁴ – Will include flow cytometry, Elispot, flow- based tetramer analysis (To be processed by [name]'s lab [name])

⁵ CBC, diff, platelets, CMP, LDH,

⁶ – This scheme will be repeated up to 4 courses

⁷ – CRP only

⁸ - Post-cycle labs will be drawn 24-72 hours after completion of the last dose of IL-2 for each cycle. These may be obtained while the patient is admitted, as long as it falls within the 24-72 hour timeframe and has been arranged with the study coordinator.

One Course is comprised of 2 cycles of high dose IL-2 followed by 4 weeks off, then 3 weeks of continuous low dose oral temozolomide, with another 2 weeks off prior to reimaging (approximately 12 weeks in duration from start to finish)

Study Schema Algorithm: Phase II Trial of High Dose Interleukin-2 followed by intermittent low dose Temozolomide in patients with Metastatic Malignant Melanoma
